5.10 Data Collection, Management and Analysis

5.10.1 Data collection, management and entry

██████████ will be responsible for data management activities for the study.

Data will be captured in a fully validated, 21 CFR Part 11 compliant Electronic Data Capture (EDC) system provided by ██████████.

██████████ will grant authorised site staff with access to the EDC system following system training and a successful competency assessment.

Data required by the protocol will first be recorded on source documents (e.g. medical records and study-specific data capture tools as needed) and then entered by site staff into the EDC system. All information in EDC must be traceable to these source documents. Any data recorded directly into EDC will be defined prior to the start of data collection. All data is currently anticipated to be associated with source data records.

Data validation checks will be activated during data entry to identify data discrepancies. Appropriate error messages will be displayed to allow modification or verification of data by the site staff.

Monitoring staff will review the data for completeness and accuracy, instructing site staff to make any required corrections or additions via data queries. ██████████ will run further automated validation checks and review the data, raising further data queries to the sites for resolution of any inconsistencies.

The Investigator will review the eCRFs for completeness and accuracy then electronically approve the data, retaining full responsibility for its accuracy and authenticity.

Medical history and adverse events will be coded using the Medical Dictionary for Regulatory Activities (MedDRA) terminology. Prior and concomitant medication will be coded using the World Health Organization Drug (WHO)-Drug Dictionary which employs the Anatomical Therapeutic Chemical (ATC) classification system.

Further coding details and data management processes will be described in a Data Management Plan (DMP).

All actions within the EDC system are captured within an audit trail. After all data, have been entered, validated and signed off, the database will be locked.

CNGB3 Gene Therapy trial for Achromatopsia

At the end of the study, PDF copies of the eCRFs for each subject and supporting information will be provided to sites and the Sponsor. The electronic data will be provided to the Sponsor.

5.10.2 Non-Adherence and Non-Retention

Participants who withdraw from the trial after the intervention will be encouraged to participate in any of the planned follow-up scheduled for the trial with their consent. Data collected prior to withdrawal will be considered in the interpretation of results.

Reasons for withdrawal from the trial will be documented on a withdrawal CRF where possible, in addition to the procedures and CRF for the final visit (6 month) assessments with the participant's consent.

5.10.3 Statistical Methods

5.10.3.1 Statistical Analysis Plan

A formal Statistical Analysis Plan (SAP) will be written by the sponsor and approved by the IDMC. This trial is an open label, no crossover, phase I/II trial involving a small number of participants, and analysis of the primary and secondary outcomes will be descriptive in nature.

5.10.3.2 Statistical Methods – Primary Outcome Analysis

The primary outcome is safety of subretinal administration of the ATIMP defined as any of the below occurring during the 6 weeks following administration, at least possibly related to the ATIMP, not surgery alone:

- Reduction in visual acuity by 15 ETDRS letters or more
- Severe unresponsive inflammation
- Infective endophthalmitis
- Ocular malignancy
- Grade III or above non-ocular SUSAR (see section 5.11.3)

The number of DLEs at each dose level will be summarised by cohort and overall.

It is anticipated that the ATIMP will be administered at the MTD in up to 15 participants (6 adults in the dose escalation phase and up to 18 further adults and children in the confirmatory safety phase). Safety data relating to these participants will allow estimation of an upper bound for the true event rate through a 95% confidence interval.

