4.3.2.2.4 Additional considerations

In the event of a DLE in one of the 3 participants at a given dose, the cohort will be expanded at the same dose level. The IDMC will review the safety data and confirm that additional participants may be treated at this dose. The IDMC may recommend that the same dose of ATIMP is administered to additional participants. The dose escalation will continue until IDMC are comfortable on review of the accumulating data, to recommend a maximum dose to be administered to children, or 3 participants have been administered the highest dose without any DLEs, or until at least 2 participants among a cohort of 3 to 6 participants experience DLEs (i.e., $\geq 33\%$ of patients with a DLE at that dose level), in which case the recommended dose will be the level below this toxic dose. In the event that 1 or 2 DLEs are seen at the first dose level, the IDMC may recommend administering a lower dose to that described in the protocol to a cohort of participants.

Table 1: Dose escalation table

Number of DLEs			
Low dose			
Participants 1-3	Participants 4-6	Action	Details
0/3		Increase	Give intermediate dose to next cohort of participants
1/3		Remain	Give low dose to another cohort of participants (Pt 4-6)
$\geq 2/3$		Stop	MTD not found. Consider lower dose
	$\leq 1/6$	Increase/stop	Has higher dose been tried? No: Give intermediate dose to next cohort of participants

Gene Therapy for Achromatopsia (CNGB3)

			Yes: MTD found – low dose
	≥ 2/6	Stop	MTD not found. Consider lower dose
Intermediate dose			
Participants 1-3	Participants 4-6	Action	Details
0/3		Increase	Give high dose to next cohort of participants
1/3		Remain	Give intermediate dose to participants 4-6
≥ 2/3		Decrease/stop	Give low dose to 3 more participants. If 6 participants already had low dose, stop. MTD found – low dose.
	≤ 1/6	Increase/stop	Has higher dose been tried? No: Give high dose to participants 1-3 Yes: MTD found – intermediate dose
	≥ 2/6	Decrease/stop	Give low dose to participants 4-6. If 6 participants already had low dose, stop. MTD found – low dose
High dose			
Participants 1-3	Participants 4-6	Action	Details
0/3		Remain	MTD found – give high dose to participants in confirmation phase
1/3		Remain	Give high dose to participants 4-6
≥ 2/3		Decrease/stop	Give intermediate dose to participants 4-6. If 6 participants already had intermediate dose, stop. MTD found – intermediate dose
	1/6	Stop	MTD found – high dose

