2. OUTCOME DEFINITIONS

2.1. Primary Safety Outcome

The primary safety outcome is defined as any of the below events occurring during the 6 weeks following administration, at least possibly related to the ATIMP, not surgery alone:

• Reduction in visual acuity by 15 Early Treatment Diabetic Retinopathy Study (ETDRS) letters or more

- Severe unresponsive inflammation (defined in Section 4.2 of the protocol)
- Infective endophthalmitis
- Ocular malignancy
- Grade III or above non-ocular suspected unexpected serious adverse reaction (SUSAR) (Protocol MGT006, Section 5.11.3.4.2 Severity or Grading of Adverse Events).

This is the same criteria as the dose limiting event in the dose escalation phase.

Overall safety will be assessed for 6 months after the intervention in this study, and a further 4.5 years in a separate long-term follow-up study (Protocol MGT007).

The adverse events preferred terms are identified in a separate file (AES_OF_INTEREST.xlsx) and saved in the ERIS system.

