3. ANALYSIS DEFINITIONS

3.1. Analysis Sets

For safety analyses, the safety analysis set includes all enrolled subjects who were administered ATIMP.

For efficacy analyses, the full analysis set includes all enrolled subjects who were administered ATIMP and have both a baseline and at least 1 visit after ATIMP administration.

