5. SAFETY ANALYSES

5.1. Primary Safety Outcome

The proportion of subjects who experience the primary safety outcome and the corresponding 95% confidence interval (CI) using for the binomial proportion based on the normal approximation with continuity correction will be provided (by age group, dose level and overall). The primary safety outcome will also be listed.

A similar analysis will also be conducted for dose-limiting events (DLEs).

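### The event-rate bound at the MTD pools expansion participants with the escalation adults whose low DLE count chose that dose, so on average the pooled rate is modestly too low

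*Protocol*

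**What the plan says.** Protocol 5.10.3.2 describes the participants at the MTD as "6 adults in the dose escalation phase and up to 18 further adults and children in the confirmatory safety phase" and continues: "Safety data relating to these participants will allow estimation of an upper bound for the true event rate through a 95% confidence interval". The same paragraph opens with a different total: "It is anticipated that the ATIMP will be administered at the MTD in up to 15 participants".

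Table 1 (Protocol 4.3.2.2.4) sets the selection. The high dose with no DLE in three adults gives "MTD found – give high dose to participants in confirmation phase". One DLE in three leads to three more adults at that dose. Two or more DLEs among three to six adults reject the dose.

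SAP 2.1 says of the primary safety outcome: "This is the same criteria as the dose limiting event in the dose escalation phase". SAP 5.1 gives the proportion and a 95% CI "for the binomial proportion based on the normal approximation with continuity correction will be provided (by age group, dose level and overall"). SAP 3.1 makes no distinction by phase: "the safety analysis set includes all enrolled subjects who were administered ATIMP".

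Part of the split by phase is already planned. Protocol 5.10.3.2 summarises DLE counts at each dose by cohort, and Protocol 4.3.2.2.5 refers to the confirmatory group as an expansion cohort. SAP 5.1 adds a listing of the outcome and a row for children, who are dosed only in the expansion. Neither document plans an event rate with a CI for expansion participants at the MTD.

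**The concern.** The escalation adults at the MTD are not an unselected binomial sample. Had they shown two or more DLEs, that dose would not be the MTD and they would not be in this pool. The variable that selects them is also the variable being estimated. Adding them to the expansion participants and computing an ordinary binomial proportion pulls the estimate down on average, and by more when the true rate is higher or the expansion group at that dose is smaller.

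This proportion and its upper limit are the trial's main numerical safety statement about the dose carried forward.

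**Working it through.** **Inputs.** Selection rule: Table 1. Pool: 6 escalation adults plus up to 18 others (Protocol 5.10.3.2). The documents give no true DLE rate p, so 5% to 30% is assumed for the bias and up to 40% for coverage. All m expansion participants are taken to be at the MTD.

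**The plan's own total.** 6 + 18 = 24, and 3 + 18 = 21 if the dose qualified on 0/3. Neither is 15; 6 + 9 = 15 is. The passage must be reconciled, so m = 18 and m = 9 are both shown.

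**Route used.** A dose qualifies on 0/3, or on 1/3 followed by 0/3. This is the high-dose route once that dose is reached. With q = 1 − p:

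- P(0/3) = q³
- P(1/3 then 0/3) = 3pq² × q³
- Share of qualifying doses that came through 0/3: w = 1 / (1 + 3pq²)

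The expected pooled rate, given that the dose qualified, is

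w × mp/(3 + m) + (1 − w) × (1 + mp)/(6 + m).

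Example, p = 0.20 and m = 18: w = 1/(1 + 0.384) = 0.7225. The rate is 0.7225 × 3.6/21 + 0.2775 × 4.6/24 = 0.1239 + 0.0532 = 17.7%.

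| True rate | w | Pooled, m = 18 | Bias (points) | Pooled, m = 9 | Bias (points) |
|---|---|---|---|---|---|
| 5% | 0.881 | 4.7% | −0.3 | 4.5% | −0.5 |
| 10% | 0.805 | 9.2% | −0.8 | 8.5% | −1.5 |
| 20% | 0.723 | 17.7% | −2.3 | 16.0% | −4.0 |
| 30% | 0.694 | 26.0% | −4.0 | 23.2% | −6.8 |

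The expansion-only rate has expectation p, so its bias is 0.

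**All Table 1 routes.** Enumerating every path, including de-escalation to a lower dose, with the same DLE rate at each dose gives 4.7%, 9.2%, 17.6% and 25.6% with m = 18, and 4.5%, 8.5%, 16.0% and 22.9% with m = 9. With DLE rates that rise with dose and m = 18, the bias runs from −0.8 to −2.7 points.

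**Not every path is biased downward.** After 1/3 then 0/3 the escalation contribution is fixed at 1/6 = 16.7%. At p = 0.10 and m = 18 the pooled expectation on that path is (1 + 1.8)/24 = 11.7%, which is too high. After 0/3 it is 1.8/21 = 8.6%, which is too low.

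**Coverage of the exact (Clopper-Pearson) upper limit, two-sided 95%, so 97.5% nominal.** Example, p = 0.25 and m = 18, where w = 0.703:

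- After 0/3, 0/21 (upper limit 16.1%) and 1/21 (23.8%) miss 25%. P(0 or 1 event in 18) = 0.75¹⁸ + 18 × 0.25 × 0.75¹⁷ = 0.0395.
- After 1/3 then 0/3, only 1/24 (21.1%) misses. P(0 events in 18) = 0.0056.
- Missed: 0.703 × 0.0395 + 0.297 × 0.0056 = 0.029. Coverage is 97.1%.
- Expansion-only: only 0/18 (18.5%) misses, so coverage is 99.4%.

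The same sum with m = 18 gives at least 98.7% at true rates of 5%, 10%, 15% and 20%. Between those points there is one short dip: just above 16.1%, the limit for 0/21, coverage is about 96.8%. It is 96.7% at 33% and lowest at about 94.8% near 37.5%. With m = 9 the lowest value up to 40% is about 93.8%. Over smaller and larger m the low points at rates of 25–40% lie at roughly 93–97%. Expansion-only coverage stays at or above 97.5%.

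**Zero-event exact upper limits**, 1 − 0.025^(1/n): 18.5% for n = 18, 16.1% for n = 21, 14.2% for n = 24.

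**The case against.** The strongest reply is that the effect is small and the data are partly visible. The unselected participants usually outnumber the selected three or six. At true rates of 10% or below with 18 expansion participants, the bias is under one point. The analysis is declared descriptive, with no hypothesis test. Cohort DLE counts, the listing and the children's row let a reader rebuild much of the split.

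Most of that stands, and it limits the point. It does not remove it. The protocol promises an upper bound for the true rate, and calling the analysis descriptive does not make that estimate unbiased. The counts and listing carry no interval. The children's row omits expansion adults and need not be confined to the MTD, since Protocol 4.3.2.2.5 allows expansion at lower levels. The IDMC may depart from Table 1, but choosing a dose on the same safety data by judgement is still selection.

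Four stronger readings are tempting and are not supported:

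- That the pooled bound is invalid. Over all Table 1 routes, with rates up to 30% when equal across doses, the exact pooled limit kept 97.6% to 100% coverage. The shortfall on the single route is a few points, mostly at high rates.
- That unselected data are nowhere shown. Only the expansion-only rate and CI are missing.
- That a dose with a true rate of 33% is generally declared the MTD 43% of the time. The figure q³(1 + 3pq²) = 0.428 is the chance of passing the high-dose rule once that dose is reached. A lower dose becomes the MTD by a different route.
- That expansion-only must replace the pooled figure as the main estimate. Few expansion participants may be at the MTD, so this is a trade-off between bias and precision.

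**Conclusion.** The point holds as a modest average downward bias in the pooled event rate at the MTD. With 18 expansion participants it is 0.3 points at a true 5% and about 4 points at a true 30%; with 9, the number implied by the stated total of 15, it is 0.5 to about 7 points. An exact upper limit loses a few points of coverage at some rates of 25–40% and little below that.

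These sizes rest on assumed DLE rates, strict use of Table 1 and every expansion participant being at the MTD. The coverage figures are for the exact interval. The normal approximation planned in SAP 5.1 is a separate and larger problem for the bound: for 0/18 its upper limit is only the continuity correction, 1/36 = 2.8%, against 18.5% exact.

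**What to change.** In SAP 5.1, for the MTD, report the event rate and 95% CI for expansion-phase participants beside the pooled figure. State that the pooled figure includes the adults used to select the dose and tends to understate the rate. Change Protocol 5.10.3.2 to match, and reconcile its total of 15 with 6 plus up to 18 in the same edit.

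The cost is one more table row and a wider interval for that row. With no events, the exact upper limit is 18.5% for 18 participants against 14.2% for 24, and wider still if fewer expansion participants are at the MTD. No change to design, dosing or data collection is needed.

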5.10.3.3 Statistical Methods – Secondary Outcome Analysis

The secondary outcomes are measures of the efficacy of the ATIMP; these will be performed on an individual participant basis and will be primarily descriptive in nature. Standard assessments will be used to measure visual function and established methods of analysis, appropriate for the assessment will be used to evaluate the data. For specialist assessments, data will be analysed by the expert team member(s) who developed the assessment. Final data will be reported descriptively.

Efficacy will be indicated by:

- 1) Any improvement in visual function from baseline that is greater than the test-retest variation for that test and is sustained for at least two consecutive assessments.

CNGB3 Gene Therapy trial for Achromatopsia

2) Any improvement in retinal function from pre – intervention assessment that is greater than test-retest variation and measurable by electrophysiology (pattern ERG, multifocal ERG or full-field ERG).

Measures will be reported individually and aggregated across participants as the proportion who satisfy the above criteria.

Quality of life patient reported outcome measures will be used to correlate a participant’s feeling about their own wellbeing with clinical observations.

Any deviations from the original statistical plan will be approved by the IDMC and described in the final report, as appropriate.

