4.1.6 Explanation for Choice of Comparators

There is no currently approved treatment for achromatopsia caused by mutations in *CNGB3*. The comparator will be the contralateral eye.

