5.4.2 Protocol defined clinical schedule

5.4.2.1 Baseline Assessments

A detailed assessment of visual function and retinal imaging of both eyes will be performed preoperatively as outlined in Section 5.6 (Table 2: Trial Assessments). For assessments requiring multiple baselines, testing is preferred on separate days within a maximum 6-month period to allow for day-to-day variation and test-retest variability for individual participants. However, it is acknowledged that a balance will be achieved between what is pragmatic and appropriate for the different tests on an individual basis. Each set of baseline measurements may take up to 3 days to perform in total. In some instances, results for protocol specified baseline tests may be available as a part of routine clinical examination within 6 months. As such, if the subject provides informed consent to use the results from the previously conducted tests, then these assessments will not need to be repeated at baseline.

Visual assessment results will be sent for reading and analysis to independent reading centres within the UK and US. For both sites imaging with OCT, fundus autofluorescence and fundus photography will be reviewed by the site teams but also sent for independent analysis by the [REDACTED], during the course of the trial. Adaptive optics images will be sent to the [REDACTED] for reading and Octopus perimetry and Microperimetry will be sent to the [REDACTED] reading centre. All images will be saved under pseudo anonymised patient identifiers and images will only be taken of the patient's eye to ensure that patients remain unidentified.

Gene Therapy for Achromatopsia (*CNGB3*)

Up to 10 mL of blood will be sampled in order to assess baseline levels of circulating antibodies against, AAV8 and of circulating antibodies against rAAV serotype 8 so that immunological responses to vector capsids can be determined following ATIMP administration (collectively described as serology in Table 2: Trial Assessments). We anticipate that that majority of participants will have no detectable pre-existing circulating antibodies against AAV8. The presence or absence of circulating antibodies will not affect recruitment of the participant. All serology tests will be performed at the Institutional Laboratory in the UK.

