5.6 Trial Assessments

Table 2: Trial assessments

	Screening	Baseline ¹			ATIMP admin	D1	D3	W1	W2	W4	W6	W12	W24
Flexibility of schedule (\pm days)		- 6 months			Day 0	\pm 0D	\pm 1D	\pm 2D	\pm 4D	\pm 7D	\pm 7D	\pm 14D	\pm 14D
Visit number	1	2	3	4	5	6	7	8	9	10	11	12	13
Informed consent	•												
Physical exam	•												
Medical history	•							•	•	•	•	•	•
Eligibility determination	•												
ATIMP administration					★								
Adverse event review		•	•	•	•	•	•	•	•	•	•	•	•
Concomitant medication review	•	•	•	•	•	•	•	•	•	•	•	•	•
Genetic screening ⁶	•												
Pregnancy test	•				•								
Vital signs ²	•	•				•		•	•	•			
Haematology		•				•		•	•	•			
Biochemistry/glucose/liver and renal function		•				•		•	•	•			
Serology		•								•		•	•
PCR						•				•			
QoL questionnaires (IVI and EQ5D-5L)		•											•
Visual acuity ³	•	•	•	•		•	•	•	•	•	•	•	•
Colour vision assessments		•	•	•								•	•
Contrast sensitivity	•	•	•	•								•	•
Reading speed		•	•	•								•	•
Static perimetry		•	•	•								•	•
Full Field Stimulus Testing		•	•	•							•	•	•
Ocular examination	•	•	•	•		•	•	•	•	•	•	•	•

CNGB3 Gene Therapy trial for Achromatopsia

	Screening	Baseline ¹			ATIMP admin	D1	D3	W1	W2	W4	W6	W12	W24
Flexibility of schedule (\pm days)		- 6 months			Day 0	\pm 0D	\pm 1D	\pm 2D	\pm 4D	\pm 7D	\pm 7D	\pm 14D	\pm 14D
Fundus photography		•				•	•	•	•	•	•	•	•
Optical coherence tomography	•	•	•	•		•	•	•	•	•	•	•	•
Adaptive optics imaging		•	•										•
Fundus autofluorescence		•	•									•	•
Pattern Electroretinography ⁴	•												•
Full field Electroretinography ⁴	•												•
Photoaversion assessments		• ⁵	• ⁵	• ⁵								•	•

¹ Baseline assessments may be performed on the same day where considered logistically and clinically appropriate

² Measurements for vital signs include: blood pressure, pulse, respiration rate, arterial oxygen saturation, temperature, height and weight

³ Visual acuity at day 1 and 3 will be assessed using the previous refraction.

⁴ ERG assessments may be performed under general anaesthesia if considered appropriate

⁵ Photoaversion Questionnaire only to be completed at one baseline visit

⁶ Not required to be repeated if previous result available from an accredited laboratory

CNGB3 Gene Therapy trial for Achromatopsia

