6.1. Changes to the SAP

The original SAP (dated 24 May 2019) described analyses of the test-retest variation for each visual function assessment, however, this will not be assessed given that the assessment of safety is the primary objective of the study and the secondary objectives for efficacy focus on the effect of the treated eye compared to the untreated eye. The statistics for the test-retest do not fit the purposes of the stated objectives and are not appropriate for the goals of the study.

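### The protocol's efficacy rule has no untreated-eye term, no closed test list and no defined threshold, so its null response rate is unknown; the SAP drops the rule without a committed replacement.

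*Protocol*

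**What the plan says.** Protocol 5.10.3.3 gives two ways in which efficacy is indicated; 5.5.2 and the structured summary carry essentially the same rule.

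- **Visual function:** "Any improvement in visual function from baseline that is greater than the test-retest variation for that test", provided that it "is sustained for at least two consecutive assessments".
- **Retinal function:** an improvement beyond test-retest variation that is "measurable by electrophysiology (pattern ERG, multifocal ERG or full-field ERG"). This has no persistence condition.

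Results are given for each person and "aggregated across participants as the proportion who satisfy the above criteria". No reference proportion is set.

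Protocol 4.1.6 says: "The comparator will be the contralateral eye". Protocol 5.4.2.1 prefers repeat baselines on separate days, to allow for day-to-day variation and "test-retest variability for individual participants". Footnote 1 to Table 2 nevertheless says: "Baseline assessments may be performed on the same day where considered logistically and clinically appropriate".

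The SAP is based on protocol v7.0. Section 6.1 drops the test-retest analysis because "the secondary objectives for efficacy focus on the effect of the treated eye compared to the untreated eye". Section 6.2 plans descriptive summaries and individual plots by eye (untreated-eye data where available). It says that mixed models comparing the eyes may be used. Section 6 sets a nominal two-sided 0.05 level.

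**The concern.** The responder rule compares each person only with his or her own baseline. Anything that moves follow-up values upward without the vector counts as response: measurement noise, practice, or a lenient threshold. Offering several tests and accepting any one of them adds further chances. The untreated eye could show how often the rule is met without vector, but it is not an input.

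A responder proportion from this rule could be read as a sign of efficacy when no one knows what proportion an inert vector would give. The SAP moves towards the right comparison but does not commit to it, and the protocol still defines efficacy the other way. Two reports of the same data could each claim to follow the plan.

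**Working it through.** The documents give no false-positive rate for this rule, so there is no figure to reproduce. The check asks what the rule gives when nothing happens.

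**Inputs from the documents**
- Seven visual-function rows in Table 2 are measured at baseline, W12 and W24: acuity, colour, contrast, reading, static perimetry, full-field stimulus testing and photoaversion.
- There are up to three baseline visits; SAP 3.2 uses their arithmetic mean.
- The structured summary places efficacy assessment at 3 to 6 months, so the two consecutive assessments are W12 and W24.
- There are up to 36 participants (protocol 5.7).

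**Assumptions not in the documents**
- Normal errors with within-subject SD Sw, baselines on separate days, no treatment effect, independent tests.
- Three candidate meanings of test-retest variation: (a) a known 95% repeatability limit, 1.96 × √2 × Sw = 2.77 Sw, above the baseline mean; (b) 2.77 times the person's own three-baseline SD above the baseline mean; (c) both follow-ups above the best baseline.

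**Visual-function criterion.** Let v be the chance that W12 and W24 both pass on one test. For (c) it is exact: the two follow-ups must be the top two of five exchangeable values, so v = 1/C(5,2) = 1/10. For (a) and (b), v comes from simulation with at least 1,000,000 draws. The chance that any of seven tests passes is 1 − (1 − v)^7.

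| Threshold | v per test | Any of 7 | Expected of 36 |
|---|---|---|---|
| (a) known 2.77 Sw | 0.03% | 0.2% | 0.1 |
| (b) 2.77 × own SD | 2.1% | 14% | 4.9 |
| (c) beats best baseline | 10% | 52% | 18.8 |

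For example, (c) gives 1 − 0.9^7 = 0.52. A between-test correlation of 0.5 lowers 52% to 37% and 14% to 12%, and leaves 0.2% unchanged.

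**Learning.** Add an upward shift at both follow-ups and recompute the any-of-7 rate.

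| Threshold | No shift | 0.5 Sw | 1 Sw |
|---|---|---|---|
| (a) | 0.2% | 1.3% | 6% |
| (b) | 14% | 30% | 52% |
| (c) | 52% | 81% | 96% |

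**Same-day baselines.** If all baselines share one day and between-day SD equals within-day SD, v rises from 2.1% to about 5.5% for (b) and from 10% to 17% for (c).

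**ERG criterion.** Table 2 has pattern and full-field ERG at screening and W24 only; multifocal ERG is named in the rule but has no row. With one value before and one after, the 95% limit gives P(Z > 1.96) = 2.5% per modality, or 1 − 0.975² = 4.9% for two. Together with (a), the participant rate is 1 − (1 − 0.0021)(1 − 0.0494) = 5.1%, or about 1.8 of 36. Under the strict threshold, nearly all null responses come from ERG.

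**What the untreated eye adds.** Apply the rule to treated-minus-untreated change, with an assumed inter-eye correlation of 0.5 and the threshold set on the difference scale. The any-of-7 rates stay at about 0.2%, 14% and 52% for shifts of 0, 0.5 and 1 Sw. The paired contrast removes learning shared by the eyes. It does not cure a lax threshold or the number of tests; those need their own remedy.

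**The case against.** The strongest reply is that the rule is no longer the operative analysis: SAP 6.1 abandons it, turns to the treated-versus-untreated comparison, and SAP 6.2 plots the eyes together. That stands, and it moves the problem. What remains is a protocol that still defines efficacy by the rule and a SAP whose between-eye model is optional.

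A reader might infer that efficacy is likely to be declared even if the vector does nothing. The documents do not support that, for four reasons.

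- The persistence condition is strong. With a known 95% limit and no learning, the visual-function criterion is met by about 0.2% of participants.
- The high figures rest on thresholds the documents do not state. The rule refers to the variation of the test, which can be read as a property of the test. Protocol 5.4.2.1 explains why repeat baselines are wanted; it does not say that each person's three values set the threshold.
- No passage says that one responder indicates efficacy for the trial. The protocol reports a proportion, the analyses are descriptive, and SAP 1.2 says there was no formal hypothesis testing.
- Seven independent tests in everyone is the full case. Several are done only where possible or available, and correlation lowers the larger figures.

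The untreated eye is also not a perfect reference. Protocol 5.4.2.2.2 treats the poorer-seeing eye, taking acuity and dominance into account, so regression to the mean can differ between eyes. That is a limitation to state, not a reason to leave the comparator out.

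**Conclusion.** The point holds as one of an uninterpretable responder proportion and a disagreement between documents. Without learning, the null rate for the visual-function criterion runs from about 0.2% to 52% per participant, depending on a threshold the plan does not give; practice effects raise it. These figures assume normal errors, three separate-day baselines and seven independent tests. The ERG criterion adds about 5% for two modalities at a 95% limit. The structural facts need no assumption: there is no untreated-eye term, test list, threshold formula or reference rate, and the replacement in the SAP is optional. Because efficacy is secondary and descriptive, this should be corrected, but it does not affect the primary safety outcome.

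**What to change.** Align protocol 5.5.2 and 5.10.3.3 with SAP 6.2:

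- Rest any statement that efficacy is indicated on a committed within-participant contrast of treated and untreated eye. Name the per-eye tests, report test by test with 95% CIs, and state that the results are exploratory and unadjusted for multiplicity.
- If the responder rule is kept, apply it identically to both eyes. Report treated eye only, untreated eye only, both and neither, with the paired difference in proportions and an exact 95% CI.
- State one threshold and its multiplier, estimated from between-day replicates pooled across participants and eyes. Leave same-day baselines out of that estimate.
- Report ERG as a paired change at W24 only, since there is no second post-treatment visit to show persistence.
- Label questionnaires and any test done with both eyes open as uncontrolled.
- Record the choice of the poorer-seeing eye as a limitation.

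The SAP describes the trial's conduct in the past tense, so a protocol amendment may come late. Protocol 5.10.3.3 already allows departures from the statistical plan to be approved by the IDMC and described in the final report, and the change could be documented that way.

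The cost is wording, one extra table and probably a less favourable reported response. Protocol 5.4.2.1 has both eyes assessed before surgery and 5.4.2.3 uses the same methods afterwards, so no new visits are needed; the SAP's caveat about availability of untreated-eye data should be checked test by test.
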